3.2 SECONDARY OBJECTIVES AND ESTIMANDS

Secondary Objective(s)

To assess the tolerability and reactogenicity profile of COVOVAX in comparison with the Control vaccine for COVISHIELD Prime, and COVAXIN Prime cohorts, separately

Estimand Description (including Endpoints)

nd Estimand 2 (for 2 and 3 listed below) of Estimand 3 (for 1 and 4 listed below)

Proportion of participants with at least one

- 1. Solicited local and/or Systemic adverse event up to 7 days post-vaccination
- 2. Unsolicited AE up to 28 days post-vaccination
- 3. SAE throughout study duration post-vaccination
- 4. Adverse event of special interest post-vaccination

A treatment policy strategy is used for assessing safety irrespective of use of immune-modifying medications/vaccinations.

An intercurrent event death will use strategy as follows:

CONFIDENTIAL Page 32 of 94

Secondary Objective(s)

Estimand Description (including Endpoints)

- Composite strategy is used for event death in case of SAE
- Solicited local and/ or systemic adverse events, unsolicited adverse events and AESI will use while on treatment strategy (i.e. data until death is utilized)

An intercurrent event COVID-19/SARS-CoV-2 infection will use Treatment policy for all listed above.

Endpoint:

- 1. Occurrence of solicited local and systemic adverse events (AEs) for 7 days post-vaccination
- 2. Occurrence of unsolicited AEs for 28 days postvaccination
- 3. Occurrence of SAEs, and adverse events of special interest (AESI) throughout the study duration following vaccination

To assess immunogenicity of Estimand 4 the COVOVAX booster dose in comparison with the Control vaccine by anti-S IgG and neutralizing antibody assays for COVISHIELD Prime. and COVAXIN Prime cohorts.

separately

GMTs and GMFR of anti-S IgG antibodies at 28, 90 and 180 days post-vaccination.

Principal stratum and Hypothetical strategy are used to understand antibody levels achieved through vaccination, without subsequent COVID-19/SARS-CoV-2 infection or use of any immune-modifying medications or other vaccines. While on treatment strategy is used for event death.

Endpoint:

Anti-S IgG antibodies at Day 29, Day 91 and Day 181

Estimand 5:

GMTs and GMFR of nAbs at 28 and 180 days postvaccination.

Principal stratum and Hypothetical strategy are used to understand antibody levels achieved through vaccination, without subsequent COVID-19/SARS-CoV-2 infection or use of any immune-modifying medications or other vaccines. While on treatment strategy is used for event death.

Endpoint:

nAbs at Day 29 and Day 181

CONFIDENTIAL Page 33 of 94

Secondary Objective(s)

To assess immune response of COVOVAX booster dose between COVISHIELD Prime, and COVAXIN Prime cohorts by anti-S IgG and neutralizing antibody assays

Estimand Description (including Endpoints)

Estimand 6:

GMTs of anti-S IgG antibodies of COVOVAX from COVISHILED prime and COVOVAX from COVAXIN prime at 28, 90 and 180 days after vaccination

Principal stratum and Hypothetical strategy are used to understand antibody levels achieved through vaccination, without subsequent COVID-19/SARS-CoV-2 infection or use of any immune-modifying medications or other vaccines. While on treatment strategy is used for event death.

Endpoint:

Anti-S IgG antibodies at Day 29, Day 91 and Day 181

Estimand 7:

GMTs of nAbs of COVOVAX from COVISHILED prime and COVOVAX from COVAXIN prime at 28 and 180 days after vaccination.

Principal stratum and Hypothetical strategy are used to understand antibody levels achieved through vaccination, without subsequent COVID-19/SARS-CoV-2 infection or use of any immune-modifying medications or other vaccines. While on treatment strategy is used for event death.

Endpoint:

nAbs at Day 29 and Day 181

To assess immune response of Covishield booster dose in COVISHIELD Prime and Covaxin booster dose in COVAXIN Prime cohorts by anti-S IgG and neutralizing antibody assays

Estimand 8:

GMTs of anti-S IgG antibodies at 28, 90 and 180 days after vaccination

Principal stratum and Hypothetical strategy are used to understand antibody levels achieved through vaccination, without subsequent COVID-19/SARS-CoV-2 infection or use of any immune-modifying medications or other vaccines. While on treatment strategy is used for event death.

Endpoint:

Anti-S IgG antibodies at Day 29, Day 91 and Day 181

Estimand 9:

GMTs of nAbs at 28 and 180 days after vaccination.

Principal stratum and Hypothetical strategy are used to understand antibody levels achieved through vaccination, without subsequent COVID-19/SARS-CoV-2 infection or use of any immune-modifying medications or other vaccines. While on treatment strategy is used for event death.

Endpoint:

nAbs at Day 29 and Day 181

CONFIDENTIAL Page 34 of 94

3.3 EXPLORATORY OBJECTIVES

Exploratory Objective(s) Estimand Description (including Endpoints) Estimand 10: To assess cell mediated The mean of change from baseline (Day 1) in cell-mediated immune response of the COVOVAX immune responses as measured by enzyme-linked immune in comparison absorbent spot (ELISpot) at 28 days and 180 days postwith the Control vaccine for vaccination **COVISHIELD** Prime. and COVAXIN Prime cohorts. separately Principal stratum and Hypothetical strategy are used to understand cell-mediated immunity achieved through vaccination, without subsequent COVID-19/SARS-CoV-2 infection or use of any immune-modifying medications or other vaccines. While on treatment strategy is used for event death. **Endpoint:** Mean of change from Baseline (Day 1) in the cell-mediated immune responses (for example, as measured by enzymelinked immune absorbent spot (ELISpot) ± intracellular cytokine staining) at Day 29 and Day 181. To assess immune response by **Estimand 11:** neutralizing antibodies against GMTs and GMFR of nAbs against variants of concern at 28 concern and 180 days post-vaccination. variants of for Principal stratum and Hypothetical strategy are used to **COVISHIELD** Prime. and understand antibody levels achieved through vaccination, COVAXIN Prime cohorts, without subsequent COVID-19/SARS-CoV-2 infection or separately use of any immune-modifying medications or other vaccines. While on treatment strategy is used for event death. **Endpoint:** nAbs against SARS-CoV-2 variants of concern at Day 29 and Day 181

Version: 4.0 Dated 21 Apr 2022

CONFIDENTIAL Page 35 of 94

4. STUDY DESIGN

This is a Phase 3, observer-blinded, randomised, active controlled study in adults ≥ 18 years of age in India who have already received primary vaccination against COVID-19 at least 6 months ago (6 months / 180 days from the second dose), to evaluate the immunogenicity and safety of the COVOVAX booster dose in comparison with the control vaccine.

Version: 4.0 Dated 21 Apr 2022

A total of 372 eligible participants of \geq 18 years of age who have completed primary 2 dose schedule of COVID-19 vaccination at least 6 months ago will be enrolled in this study in 2 cohorts of 186 participants each with 1:1 allocation to COVOVAX or control vaccine. Two cohorts of 186 participants each will be as below:

- **COVISHIELD Prime cohort:** Primary vaccination with two doses of COVISHIELD
- **COVAXIN Prime cohort:** Primary vaccination with two doses of COVAXIN

All eligible participants (n=372) will receive a single dose of 0.5 mL of either COVOVAX or Control vaccine on Day 1 as per randomization. Post vaccination site visits are planned on Day 29, Day 91, and Day 181.

Treatment allocation:

COVISHIELD Prime cohort	COVOVAX	93
	Covishield	93
COVAXIN Prime cohort	COVOVAX	93
	Covaxin	93

Approximately 10 ml blood sample will be collected at baseline (Day 1), Day 29, Day 91 and Day 181. Additionally, up to 20 ml blood sample may be collected from subset of 36 participants (18 from each of the two prime cohorts) for assessment of CMI responses at baseline, Day 29 and Day 181.

CONFIDENTIAL Page 36 of 94

Table 1: Schedule of study events

Visit Number	1	2	3	4
Visit time and window	Day 1	Day 29 (+7)	Day 91 (+7)	Day 181 (+14)
Informed Consent	X		NA	En
Demographic Data	X		NA	
Medical History including details of COVID-19 Vaccination	X		NA	
General Physical Examination & vital signs	X	Xa	Xª	Xa
Urine pregnancy test ^b	X	20.0	NA	
Inclusion/Exclusion Criteria	X	NA		
Randomization	X	NA		
Nasopharyngeal /Nose and/or throat swab for RT-PCR	X	Xc		
Blood collection for immunogenicity assessments	X	x x x		X
Study Vaccination	X	NA		Apa
30-Minute Post-Vaccination Assessment	X	NA		
Recording of solicited AEs		7 days post- cination		
Recording of unsolicited AEs	2.00	ough 28 days post- vaccination		NA
Reporting of SAEs, AESI	Throughout the study			
Recording of concomitant medications and vaccinations ^d		Throughout the study		

CONFIDENTIAL Page 37 of 94

a. A targeted physical examination (only at post vaccination visits) will be performed if there has been any AE reported since the previous visit that has not already been recorded and closed within unscheduled visits

b. Only among female participants of child bearing potential.

C. Post-vaccination: If the participant presents with qualifying symptoms of suspected COVID-19 disease [Appendix II, Table 1] OR history of contact with a confirmed COVID-19 positive case then a swab from nasopharynx / nose and/or throat will be collected for RT-PCR testing for SARS-CoV-2 infection.

d. Beyond Day 29, only the concomitant medications indicated for SAEs and AESI, if any will be recorded

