7.6.2 Concomitant Medications and Vaccines

At each study visit, the investigator/designee will ask the participants about any prescription or over-the-counter medication(s) taken since the last visit. Any medications taken at any time during the study period must be recorded on source documents and the eCRF with trade and/or generic name, indication, dose, start and end dates until Day 29. Beyond Day 29, only medications taken for SAE / AESI will be recorded.

Any treatments and/or medications specifically contraindicated, e.g., any investigational or non-registered product, any immunosuppressant and immune-modifying drug including systemic steroids, any immunoglobulin and blood product should be checked at each study visit subsequent to the study vaccination. If any become applicable during the study, it will not

CONFIDENTIAL Page 51 of 94

require withdrawal of the participant from the study but may determine a participant's evaluability in the per-protocol analysis.

Any vaccine not foreseen in the study protocol in the period starting at Visit 1 (Day 1) and ending at end of study visit must be recorded in the eCRF.

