10.5.5 Per Protocol Population

Per Protocol population will be a subset of Full Analysis population. Per Protocol population consist of all participants who received the study vaccine and provided an evaluable serum sample post vaccination for at least one assessment and have baseline (Day 1) data available, excluding any data from time points following a SARS-CoV-2 infection or major protocol deviation (defined as use of an immunosuppressant, immune-modulating medication or vaccines which interfere with assessing immunogenicity), which means subject exclusion when any of these event(s) occurs before Day 29. All immunogenicity analyses will be performed using this population. Participants in the Per Protocol population will be analyzed 'as randomized' (i.e. planned vaccine group). The review and determination for exclusion from the Per Protocol Population will be carried out in a blinded fashion by a study clinician prior to unblinding.

CONFIDENTIAL Page 63 of 94

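### After Day 29 the protocol limits medication recording to SAE/AESI treatment but needs all immune-modifier use through Day 181, so the Day 91 and Day 181 estimands cannot be reliably applied

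*Protocol*

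**What the plan says.** **Recording.** Table 1 (section 4) has a row "Recording of concomitant medications and vaccinations", scheduled for the whole study but qualified by footnote d: "Beyond Day 29, only the concomitant medications indicated for SAEs and AESI, if any will be recorded". The first paragraph of section 7.6.2 asks for full details of every medication (name, indication, dose, dates) up to Day 29, and then says: "Beyond Day 29, only medications taken for SAE / AESI will be recorded".

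**Checking.** The second paragraph of 7.6.2 deals with contraindicated treatments. It says that "any immunosuppressant and immune-modifying drug including systemic steroids, any immunoglobulin and blood product should be checked at each study visit subsequent to the study vaccination". Such use will not "require withdrawal of the participant from the study but may determine a participant's evaluability in the per-protocol analysis". The section then requires any vaccine outside the protocol to be recorded from Visit 1, "ending at end of study visit must be recorded in the eCRF".

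**Analysis.** Estimands 4 to 9 (section 3.2) describe antibody levels "without subsequent COVID-19/SARS-CoV-2 infection or use of any immune-modifying medications or other vaccines". Estimands 10 and 11 (section 3.3) use the same condition. Section 10.6.1 lists use of immunosuppressants, immune modifiers or interfering vaccines as an intercurrent event (IcEv2), with no limit by indication. Section 10.5.5 drops data from time points after a SARS-CoV-2 infection or a major protocol deviation, the latter "defined as use of an immunosuppressant, immune-modulating medication or vaccines which interfere with assessing immunogenicity".

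**The concern.** The analysis rules need to know, up to Day 181, whether a participant took an immune modifier and whether that came before a given sample. The recording rule, stated twice, stops general capture at Day 29. A systemic steroid course or an immunoglobulin given later for a condition that is neither an SAE nor an AESI falls outside what must be recorded.

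At stake is whether the Day 91 and Day 181 titres and cell-mediated responses match their definition, which is a response free of immune modifiers. Sites that follow footnote d and sites that follow the check in 7.6.2 would also capture different things. A later analysis plan cannot mend this, because it cannot restore information that was never collected.

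**Working it through.** No sample size, power or error rate enters, and there is no stated figure to reproduce. The check sets the protocol's sections side by side.

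1. **What the analysis needs.** Estimands 4, 6 and 8 cover anti-S IgG at Days 29, 91 and 181. Estimands 5, 7, 9 and 11 cover neutralizing antibodies, and Estimand 10 cell-mediated responses, at Days 29 and 181. Section 10.6.2 applies the principal stratum to intercurrent events before Day 29, so later events fall to the hypothetical strategy. Section 10.5.5 removes time points after the event. Both the fact of use and its order relative to each sample are therefore required.

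2. **What must be recorded after Day 29.** Medication given for an SAE or AESI is recorded (footnote d; 7.6.2, first paragraph), and so is any non-study vaccine (7.6.2, last paragraph). For immune-modifying drugs given for other reasons, 7.6.2 requires a check but names no eCRF entry, drug detail or date.

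3. **Whether adverse-event data fill the gap.** They do not. Unsolicited AEs are collected through 28 days (section 9.5). After that only SAEs and AESIs are collected, so the illness that prompted the drug would not be in the database either.

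4. **A worked case.** Suppose a systemic steroid course starts on Day 60 for a non-serious, non-AESI condition.
   - Under 10.5.5, the Day 91 and Day 181 values should be dropped.
   - Under footnote d and the first paragraph of 7.6.2, the course is not recorded.
   - Under the second paragraph of 7.6.2, staff check for it at Visit 3, but nothing says where the answer goes.
   - If the course started on Day 120 instead, only Day 181 should be dropped, so the two cases must be told apart.

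5. **Day 29.** All medications are recorded until then, so the Day 29 co-primary analyses have the information they need.

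6. **Size.** The protocol gives no rate of immune-modifier use after Day 29. Purely as an assumption, 2% to 5% use would mean 0.02 × 79 = 1.6 to 0.05 × 79 = 4.0 participants per arm, taking the 79 evaluable per arm of section 10.4. If, again by assumption, 4 of 79 had their titre halved, that arm's GMT would be multiplied by 2^(−4/79) = 0.966, a fall of about 3.4%. Neither the rate nor the halving has support in the protocol, so these figures illustrate scale and are not an estimate.

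**The case against.** The strongest reply is that the second paragraph of 7.6.2 is a specific rule for exactly these drugs, and that the sentence before it concerns medication in general. A check that may decide per-protocol evaluability must be meant to reach the analysis. In section 7.2, the Visit 3 and Visit 4 interviews ask about any concomitant medication since the last visit, without an SAE/AESI limit, and sites are told to transcribe all information to the eCRF. Exclusion criteria 8 and 9 bar planned chronic immunosuppression, immunoglobulin and blood products, which leaves mainly short or unplanned courses. Use that interferes with immunogenicity is also a major protocol deviation under 10.5.5, reviewed by a study clinician before unblinding.

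Much of this stands. A reader might infer that such drugs are never captured, that affected participants cannot be found, or that the estimands cannot be applied at all. The protocol does not support that: the visit checks and interviews give a route to the information, at least in source documents. Nor is there a complete absence of recording from Day 30 to Day 181, since SAE/AESI medication and all vaccines are recorded.

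What the reply does not do is remove the conflict. 7.6.2 says the drugs are checked, while for vaccines it explicitly requires an eCRF record. The open interview question and transcription instruction in 7.2 pull against footnote d. A recorded yes/no answer at each visit would place the use between two visits and support a rough exclusion, but the protocol does not require even that to be entered. If use is first disclosed at Visit 4, only a start date shows whether it came before the Day 91 sample.

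**Conclusion.** The point holds as an internal inconsistency in data capture. Under the rules as written, immune-modifier use after Day 29 for a condition that is neither an SAE nor an AESI may go unrecorded or undated. The Day 91 and Day 181 parts of Estimands 4 to 11 therefore cannot be reliably applied. It concerns the drug part of one intercurrent event; vaccines are recorded to the end of study, and the recording of infection and death is not at issue.

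The consequence is limited. All estimands concerned are secondary or exploratory, and none carries a non-inferiority criterion at Day 91 or Day 181. The four co-primary tests in each cohort are at Day 29 and are unaffected. This takes Day 29 in the recording rule to mean Visit 2, which has a +7 day window and collects concomitant medication before the blood sample.

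A reader might want to size the problem by the calendar share of follow-up after Day 29 or by an assumed rate of use. Neither works: time elapsed is not bias, and the protocol contains no rate. The number of affected values is unknown, and similar use in both arms would largely cancel in a comparison between them. It is still worth correcting, because the remedy is small and missing dates are hard to recover later.

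**What to change.** Reconcile footnote d of Table 1 with both paragraphs of 7.6.2. State that every immunosuppressant, immune-modifying drug (including systemic corticosteroids), immunoglobulin and blood product is recorded in the eCRF, with start and stop dates, through Day 181 and regardless of indication. Keep the SAE/AESI restriction for all other medication after Day 29. Align the interview wording for Visits 3 and 4 in section 7.2 with this.

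The cost is one additional eCRF entry at each of Visits 3 and 4, where staff are already told to check for these drugs. The change concerns data capture only and alters no rule on treatment or withdrawal.

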5. STUDY POPULATION

5.1 INCLUSION CRITERIA

Eligible participants must meet all of the below criteria at the time of enrolment:

- 1. Adults aged \geq 18 years of either sex
- 2. Written informed consent by participants
- 3. Those who have completed primary COVID-19 vaccination schedule with either Covishield or Covaxin (2 doses) at least 6 months ago (6 months / 180 days from the second dose)
- 4. The participant is resident of the study area and is willing to comply with study protocol requirements, including availability for all scheduled visits of the study
- 5. Healthy / clinically stable condition, as determined by medical history and physical examination
- 6. Sexually active female participants of childbearing potential* must have practiced adequate contraception for 28 days prior to study vaccine administration and agree to continue adequate contraception until completion of 28 days after vaccination
 - * Females can be considered not of childbearing potential only if they have undergone bilateral tubal ligation or occlusion, or hysterectomy, or bilateral oophorectomy, or are post-menopausal (defined as continuous amenorrhea for 12 months)
- 7. Female participants of childbearing potential must have a negative urine pregnancy test within 24 hours prior to study vaccine administration

5.2 EXCLUSION CRITERIA

Participants meeting any of the below criteria at the time of enrolment will be ineligible to participate in the trial:

- 1. Acute illness including COVID-19 with or without fever at the time of screening
- History of laboratory confirmed (by RT-PCR, rapid antigen test or serology to SARS-CoV-2) COVID-19
- 3. History of allergic reactions after previous vaccinations
- 4. Hypersensitivity to any component of study vaccines
- 5. Any confirmed or suspected condition with impaired/altered function of immune system (e.g. immunodeficient or autoimmune conditions)

Confidential Page 38 of 94

Note: Stable endocrine disorders that have a confirmed autoimmune etiology (e.g., thyroid, pancreatic) are allowed.

- 6. Have any bleeding disorder which is considered as a contraindication to intramuscular injection or blood draw
- 7. Suspected or known current alcohol or drug dependence
- 8. Chronic administration (defined as more than 14 continuous days) of immunosuppressant or other immune-modifying drugs within three months prior to the study vaccination or planned use throughout the study period (For corticosteroids, this means prednisone, or equivalent, ≥ 0.5 mg/kg per day. Inhaled, intranasal and topical steroids are allowed)
- 9. Administration of blood, blood products and/or plasma derivatives or any parenteral immunoglobulin preparation in the past 3 months or planned use throughout the study period
- 10. Continuous use of anticoagulants, such as coumarins and related anticoagulants (i.e. warfarin) or novel oral anticoagulants (i.e. apixaban, rivaroxaban, dabigatran and edoxaban etc)
- 11. Administration of any vaccine within 28 days prior to enrolment in the study or planned administration of any vaccine for until 28 days after study vaccination
- 12. Planning to receive a booster dose of COVID-19 vaccine during the course of the study
- 13. Prior receipt of a booster dose of COVID-19 vaccine
- 14. Use of any investigational or non-registered drug or vaccine within 30 days prior to the administration of study vaccines or planned during the study
- 15. Pregnant or breast-feeding
- 16. Acute or chronic, clinically significant pulmonary, cardiovascular, endocrine, metabolic, gastrointestinal, neurological, hepatic, renal functional abnormality or any other systemic disorder, that are assessed by the investigator (based on medical history or physical examination) as being clinically unstable within the prior 4 weeks (mild or moderate well-controlled comorbidities are allowed)
- 17. History of chronic neurological disorders such as multiple sclerosis, dementia, transient ischemic attacks, Parkinson's disease, degenerative neurological conditions, neuropathy, and epilepsy or a history of stroke or previous neurological disorder within 12 months with residual symptoms

CONFIDENTIAL Page 39 of 94

Note: Participants with a history of migraine or chronic headaches or nerve root compression that have been stable on treatment for the last 4 weeks not to be excluded

18. Any other condition that in the opinion of the investigator would jeopardize the safety or rights of the participant in the study or make it unlikely that the participant could complete the protocol

